## Appendix A. Algorithms for Days of OUDs Treatment

### A1. Operationalization to Estimate Number of Patient-days of Treatment for Opioid Use Disorders from Electronic Health Records and Claims Data

The data used to estimate patient-days of treatment for OUD can include medication orders from the EHR, and procedure codes from the EHR. Medication dispensings from pharmacy claims and the EHR will be considered in sensitivity analyses only. Medication orders (and dispensings) commonly include variables for the drug name (generic and/or brand); date dispensed/ordered; quantity dispensed or ordered; intended days' supply (dispensings only); directions for use (used to estimate days' supply for orders); strength per unit; and prescriber. Procedure data includes the drug name, strength, date administered, and provider. Using the data noted above, we estimate runout dates (date when the OUD treatment days provided by that particular dispensing/order/procedure ends) for each order/procedure (and dispensings in sensitivity analyses) of OUD treatment (buprenorphine [Table A1] and naltrexone) by adding the intended or estimated days' supply to the start date (date of dispensing, order, or procedure). Sublocade and naltrexone injections are assumed to provide 28 days of OUD treatment (i.e., days' supply=28). Probuphine is assumed to provide 6 months of treatment. Each unique order, and procedure (and dispensings when included), are then combined into an episode or episodes (if gaps) of OUD treatment. Episodes are then summed to calculate the total patient days covered with OUD treatment in a given time period. See Section A3 for details on how episodes are estimated from the unique orders and procedures (and dispensings when included).

Often data obtained from clinical and/or administrative systems confronts us with missing data fields (i.e., quantity dispensed/ordered or intended days' supply) or situations that would be very unlikely or impossible, such as an unrealistic daily dose of buprenorphine or a day's supply greater than 6 months for a controlled substance. Therefore, as part of Phase 1 of CTN-0074, we developed data cleaning rules to address these situations. Section A2 outlines some of the key situational assumptions.

Table A1: Buprenorphine Formulations Included for OUD Treatment		
Medication Name(s)	Route of Administration (form)	Strength in Milligrams (mg)
Buprenorphine (Brands: Subutex®)	Sublingual tablet and film	2 mg, 8 mg
Buprenorphine/naloxone (Brands: Suboxone®, Cassipa®)	Sublingual tablet and film	2 mg/0.5 mg, 4mg/1mg, 8 mg/2 mg, 12mg/3mg, 16mg/4mg
Bunavail® (buprenorphine/naloxone)	Buccal film	2.1 mg/0.3 mg, 4.2 mg/0.7 mg, 6.3 mg/1 mg
Buprenorphine/naloxone (Brand: Zubsolv®)	Sublingual tablet	1.4 mg/0.36 mg, 2.9 mg/0.71 mg, 5.7 mg/1.4 mg, 8.6 mg/2.1 mg, 11.4 mg/2.9 mg
Buprenorphine (Brand: Probuphine®)	Subdermal implants	4 single rods each 74.2 mg
Buprenorphine (Brand: Sublocade)	Subcutaneous injection	100 , 300 mg

## A2. Data Cleaning and Quality Checks for Individual Oral Buprenorphine Orders (and dispensings for sensitivity analyses)

Variables	Definition
Sid	Unique study id
rxname	Drug name (e.g., buprenorphine, naltrexone, buprenorphine and naloxone)
rxamt	Quantity ordered (e.g., 30 tablets)
rxsup	Supply of the order or how long the order should last (e.g., 30 days) This is determined for orders by 1) converting SIG (directions for use) into pills per day (PPD). For example, “take 1 tablet twice a day” is 2 PPD; 2) dividing the rxamt by ppd. For example, an order for rxamt=30 that has PPD=2 would have a rxsup=30/2 or 15 days. Days supply is then rounded to nearest whole number.
strength	Mg in one dose (e.g., 8 mg)
daily dose (DD)	=PPD * strength, for example, 2 PPD of 8 mg bup is 16 mg/day.
date	Date medication was ordered or dispensed

- 1) Summarize duplicates for orders. Duplicates defined as orders for the same **patient (sid)** with same rxname, date, and strength.
  - Number of total orders =
  - Number of unique subjects =
  - Number of subjects with at least 1 duplicate pair:
  - Percent of subjects with at least 1 duplicate pair:
  - Number of total orders that are considered a potential duplicate =
    - Example: 6 orders for the same patient where orders 1&2 have the same rxname, order date, and strength, and orders 3-5 also have the same rxname, date, and strength. This is a total of 5 duplicates. The percent of duplicate pairs across all this patient’s orders is 5 divided by 6 (total number of orders).
  - Percent of duplicate pairs across total orders:
- 2) Provide potential duplicates to health systems and ask that they chart review and de-dupe where needed (data anomaly) or provide revised order “date” if they are not duplicates
- 3) **De-dupe remaining duplicates.** If rxsup is different or 1+ is missing, keep the one with the largest rxsup. If rxsup is the same but quantity differs, keep the one with the largest quantity. If rxsup and quantity are the same across dupes, randomly keep one order.
  - Number of total orders =
  - Number of unique subjects (should not change):
- 4) Derive a pills per day (PPD) variable =Rxamt / Rxsup for each bup rx where rxamt and rxsup are known and reasonable (not missing, not zero, not <1).

- 5) Calculate daily dose (DD) variable = PPD x strength (where strength is known). Round DD to an integer for each bup rx.
- 6) Set missing refills to = 0
- 7) Provide frequencies in table 1 and table 2 below for buprenorphine. This is post de-dupe. (The days supply in health system C are calculated as quantity/ppd before calculating the frequencies. They are originally missing.)

Table 1a. Proportion of orders and unique individuals with data anomalies		
	No. bup orders=	No. subjects=
	n (%)	
Missing		
Strength		
DD		
Rxsup		
Rxamt		
Both rxsup & rxamt		
Missing strength, rxsup, & rxamt		
Zero value		
Rxsup		
Rxamt		
Both Rxsup & rxamt		
<0 as a value		
Rxsup		
Rxamt		
Both Rxsup & rxamt		
Specific cut points		
DD>40		
DD>40 in 3+ consecutive Rx		
DD>40 in < 3 consecutive Rx		
Rxsup<1		
Rxsup>30		
Rxsup >60		
Rxsup>90		
Rxsup>180		
Rxsup=1 & DD>8 mg		
Refills ≥1		
Refills >6		

Table 1a. Proportion of orders and unique individuals with data anomalies		
	No. bup orders=	No. subjects=
	n (%)	
Rxamt<1		
Rxamt=1		
Rxamt >30		
Rxamt >60		
Rxamt >90		

Table 2a. Distribution of values for raw variables of interest						
	Min	25th	50th	75th	Max	% above 3 times 75th percentile
DD						
Strength						
Rxamt						
Rxsup						
Refills						

- 8) Output all bup orders for subjects with outliers (defined as above 3 x the 75th percentile) for rxsup and/or rxamt.
- 9) Output all bup orders for subjects with rxup and/or rxamt less than 1.
- 10) Co-I reviews all bup orders identified in steps 7 and 8 to flag which outliers are likely legit and should not be imputed. Co-I to determine if and what to impute for rxsup or rxamt <1.
- 11) For rxsup and rxamt outliers that are to be imputed and for rxsup and rxamt values <1 that are to be imputed, set to missing.
- 12) Impute all missing rxsup and rxamt as follows below. We do not need to impute refills, strength, ppd, or DD.
  - Use the most common value from the same patient's bup rx w/in +/- 100 days of missing field Take the value closest to missing if there is a tie in the # of occurrences. If tie in both, use the smallest value.
  - If the patient has no other bup rx w/in +/- 100 days of the missing, impute the median value from all bup rx at that health system. If all bup rx are missing the field at that health system, impute the median value from all bup rx at all health systems.

13) Populate Table 1b and 2b below (post imputation of bup)

Table 1b. Proportion of buprenorphine orders and unique individuals with data anomalies		
	No. bup orders=	No. subjects=
	n (%)	
Specific cut points		
DD>40		
DD>40 in 3+ consecutive Rx		
DD>40 in < 3 consecutive Rx		
Rxsup<1		
Rxsup>30		
Rxsup >60		
Rxsup>90		
Rxsup>180		
Rxsup=1 & DD>8 mg		
Refills ≥1		
Refills >6		
Rxamt<1		
Rxamt=1		
Rxamt >30		
Rxamt >60		
Rxamt >90		

Table 2b. Distribution of values for raw variables of interest that were imputed					
	Min	25th	50th	75th	Max
Rxamt					
Rxsup					

14) Pull in buprenorphine (J0570, G2070, G2072, Q9991, Q9992, G2068, G2079, G2069, J0571, J0572, J0573, J0574, J057), injectable naltrexone (J2315, G2073, HZ84ZZZ, HZ94ZZZ), and methadone maintenance therapy (HZ91ZZZ, HZ81ZZZ, H0020, G2067, G2078) procedures from procedures data tables and injectable naltrexone (defined as brand= Vivitrol or route=intramuscular) from medication order tables.

Procedure data	Number of occurrences	Unique number of patients
Implant probuphine - J0570, G2070, G2072		
Sublocade - Q9991, Q9992, or G2069		
Oral bup - J0571, J0572, J0573, J0574, or J0575, G2068, G2079		
Oral bup procedure codes after adding up ones billed on same day (see Step 14)		
XR injectable naltrexone procedures (J2315, G2073, HZ84ZZZ, HZ94ZZZ)		
XR injectable naltrexone from medication orders		
Methadone maintenance therapy (HZ91ZZZ, HZ81ZZZ, H0020, G2067, G2078)		

15) Create a start and end date for each bup rx and procedure

- Start date=rxdate (orders) or adate (procedures)
- For bup orders: End date= (rxdate + rxsup) -1
  - If refills, multiply rxsup by number of refills +1 to calculate the end date. For example, an order with one refill and rxsup=30 would be  $30*2 = 60$  days. An order with 2 refills and rxsup=30 would be  $30*3=90$  days.
- For oral bup procedures (J0571, J0572, J0573, J0574, J0575), set rxsup=1 and enddate=(adate + rxsup)-1. Essentially, each procedure code for oral med covers 1 day. If duplicates (same day for any of these 5 codes), add them together and then keep 1. For example, a subject with 3 oral bup codes (any not distinct codes) on 1/1/2020 would have a start date of 1/1/2020 and rxsup=3. Keep just one of these records with rxsup=3 and enddate=(1/1/2020 + 3) -1 or 1/3/2020
- For oral bup procedures (G2068 or G2079), set rxsup=7 and enddate=adate + rxsup -1
- For procedures J0570, G2070, G2072: (buprenorphine rods; brand is probuphine): enddate=adate+179 days
- For procedure Q9991, Q9992, or G2069 (Sub Q buprenorphine; brand is sublocade): enddate=adate + 27 days
- For injectable naltrexone (from procedure codes J2315, G2073 or naltrexone XR injectable orders (brand=Vivitrol or route=intramuscular): enddate=adate (procedure) or rxdate (order) + 27 days
- Define the list of OUD ICD-9 and ICD-10 diagnosis codes
 

Opioid abuse	F11.1
Opioid abuse, uncomplicated	F11.10
Opioid abuse, in remission	F11.11

Opioid abuse with intoxication	F11.12
Opioid abuse with intoxication, uncomplicated	F11.120
Opioid abuse with intoxication delirium	F11.121
Opioid abuse with intoxication with perceptual disturbance	F11.122
Opioid abuse with intoxication, unspecified	F11.129
Opioid abuse with opioid-induced mood disorder	F11.14
Opioid abuse with opioid-induced psychotic disorder	F11.15
Opioid abuse with opioid-induced psychotic disorder with delusions	F11.150
Opioid abuse with opioid-induced psychotic disorder with hallucinations	F11.151
Opioid abuse with opioid-induced psychotic disorder, unspecified	F11.159
Opioid abuse with opioid-induced disorder	F11.18
Opioid abuse with opioid-induced sexual dysfunction	F11.181
Opioid abuse with opioid-induced sleep disorder	F11.182
Opioid abuse with other opioid-induced disorder	F11.188
Opioid abuse with unspecified opioid-induced disorder	F11.19
Opioid dependence, uncomplicated	F11.20
Opioid dependence, in remission	F11.21
Opioid dependence with intoxication, uncomplicated	F11.220
Opioid dependence with intoxication delirium	F11.221
Opioid dependence with intoxication with perceptual disturbance	F11.222
Opioid dependence with intoxication, unspecified	F11.229
Opioid dependence with withdrawal	F11.23
Opioid dependence with opioid-induced mood disorder	F11.24
Opioid dependence with opioid-induced psychotic disorder with delusions	F11.250
Opioid dependence with opioid-induced psychotic disorder with hallucination	F11.251
Opioid dependence with opioid-induced psychotic disorder, unspecified	F11.259
Opioid dependence with other opioid-induced disorder	F11.28
Opioid dependence with opioid-induced sexual dysfunction	F11.281
Opioid dependence with opioid-induced sleep disorder	F11.282
Opioid dependence with other opioid-induced disorder	F11.288
Opioid dependence with unspecified opioid-induced disorder	F11.29
Opioid type dependence, unspecified	304.00
Opioid type dependence, continuous	304.01
Opioid type dependence, episodic	304.02
Opioid type dependence, in remission	304.03
Combinations of opioid type drug with any other drug dependence, unspecified	304.70
Combinations of opioid type drug with any other drug dependence, continuous	304.71
Combinations of opioid type drug with any other drug dependence, episodic	304.72
Combinations of opioid type drug with any other drug dependence, in remission	304.73
Opioid abuse, unspecified	305.50

Opioid abuse, continuous	305.51
Opioid abuse, episodic	305.52
Opioid abuse, in remission	305.53
• Define the list of opioid overdose ICD-9 and ICD-10 diagnosis codes	
Poisoning by, adverse effect of and underdosing of opium	T40.0
Poisoning by, adverse effect of and underdosing of opium	T40.0X
Poisoning by opium, accidental (unintentional)	T40.0X1
Poisoning by opium, accidental (unintentional), initial encounter	T40.0X1A
Poisoning by opium, accidental (unintentional), subsequent encounter	T40.0X1D
Poisoning by opium, accidental (unintentional), sequela	T40.0X1S
Poisoning by opium, intentional self-harm	T40.0X2
Poisoning by opium, intentional self-harm, initial encounter	T40.0X2A
Poisoning by opium, intentional self-harm, subsequent encounter	T40.0X2D
Poisoning by opium, intentional self-harm, sequela	T40.0X2S
Poisoning by opium, assault	T40.0X3
Poisoning by opium, assault, initial encounter	T40.0X3A
Poisoning by opium, assault, subsequent encounter	T40.0X3D
Poisoning by opium, assault, sequela	T40.0X3S
Poisoning by opium, undetermined	T40.0X4
Poisoning by opium, undetermined, initial encounter	T40.0X4A
Poisoning by opium, undetermined, subsequent encounter	T40.0X4D
Poisoning by opium, undetermined, sequela	T40.0X4S
Poisoning by and adverse effect of heroin	T40.1
Poisoning by and adverse effect of heroin	T40.1X
Poisoning by heroin, accidental (unintentional)	T40.1X1
Poisoning by heroin, accidental (unintentional), initial encounter	T40.1X1A
Poisoning by heroin, accidental (unintentional), subsequent encounter	T40.1X1D
Poisoning by heroin, accidental (unintentional), sequela	T40.1X1S
Poisoning by heroin, intentional self-harm,	T40.1X2
Poisoning by heroin, intentional self-harm, initial encounter	T40.1X2A
Poisoning by heroin, intentional self-harm, subsequent encounter	T40.1X2D
Poisoning by heroin, intentional self-harm, sequela	T40.1X2S
Poisoning by heroin, assault	T40.1X3
Poisoning by heroin, assault, initial encounter	T40.1X3A
Poisoning by heroin, assault, subsequent encounter	T40.1X3D
Poisoning by heroin, assault, sequela	T40.1X3S
Poisoning by heroin, undetermined	T40.1X4
Poisoning by heroin, undetermined, initial encounter	T40.1X4A
Poisoning by heroin, undetermined, subsequent encounter	T40.1X4D
Poisoning by heroin, undetermined, sequela	T40.1X4S
Poisoning by, adverse effect of and underdosing of other opioids	T40.2
Poisoning by, adverse effect of and underdosing of other opioids	T40.2X

Poisoning by other opioids, accidental (unintentional)	T40.2X1
Poisoning by other opioids, accidental (unintentional), initial encounter	T40.2X1A
Poisoning by other opioids, accidental (unintentional), subsequent encounter	T40.2X1D
Poisoning by other opioids, accidental (unintentional), sequela	T40.2X1S
Poisoning by other opioids, intentional self-harm,	T40.2X2
Poisoning by other opioids, intentional self-harm, initial encounter	T40.2X2A
Poisoning by other opioids, intentional self-harm, subsequent encounter	T40.2X2D
Poisoning by other opioids, intentional self-harm, sequela	T40.2X2S
Poisoning by other opioids, assault	T40.2X3
Poisoning by other opioids, assault, initial encounter	T40.2X3A
Poisoning by other opioids, assault, subsequent encounter	T40.2X3D
Poisoning by other opioids, assault, sequela	T40.2X3S
Poisoning by other opioids, undetermined	T40.2X4
Poisoning by other opioids, undetermined, initial encounter	T40.2X4A
Poisoning by other opioids, undetermined, subsequent encounter	T40.2X4D
Poisoning by other opioids, undetermined, sequela	T40.2X4S
Poisoning by methadone, accidental (unintentional)	T40.3X1
Poisoning by methadone, accidental (unintentional), initial encounter	T40.3X1A
Poisoning by methadone, accidental (unintentional), subsequent encounter	T40.3X1D
Poisoning by methadone, accidental (unintentional), sequela	T40.3X1S
Poisoning by methadone, intentional self-harm, initial encounter	T40.3X2
Poisoning by methadone, intentional self-harm, initial encounter	T40.3X2A
Poisoning by methadone, intentional self-harm, subsequent encounter	T40.3X2D
Poisoning by methadone, intentional self-harm, sequela	T40.3X2S
Poisoning by methadone, assault	T40.3X3
Poisoning by methadone, assault, initial encounter	T40.3X3A
Poisoning by methadone, assault, subsequent encounter	T40.3X3D
Poisoning by methadone, assault, sequela	T40.3X3S
Poisoning by methadone, undetermined	T40.3X4
Poisoning by methadone, undetermined, initial encounter	T40.3X4A
Poisoning by methadone, undetermined, subsequent encounter	T40.3X4D
Poisoning by methadone, undetermined, sequela	T40.3X4S
Poisoning by other synthetic narcotics, accidental (unintentional)	T40.4X1
Poisoning by other synthetic narcotics, accidental (unintentional), initial encounter	T40.4X1A
Poisoning by other synthetic narcotics, accidental (unintentional), subsequent encounter	T40.4X1D
Poisoning by other synthetic narcotics, accidental (unintentional), sequela	T40.4X1S
Poisoning by other synthetic narcotics, intentional self-harm	T40.4X2
Poisoning by other synthetic narcotics, intentional self-harm, initial encounter	T40.4X2A
Poisoning by other synthetic narcotics, intentional self-harm, subsequent encounter	T40.4X2D

Poisoning by other synthetic narcotics, intentional self-harm, sequela	T40.4X2S
Poisoning by other synthetic narcotics, assault	T40.4X3
Poisoning by other synthetic narcotics, assault, initial encounter	T40.4X3A
Poisoning by other synthetic narcotics, assault, subsequent encounter	T40.4X3D
Poisoning by other synthetic narcotics, assault, sequela	T40.4X3S
Poisoning by other synthetic narcotics, undetermined	T40.4X4
Poisoning by other synthetic narcotics, undetermined, initial encounter	T40.4X4A
Poisoning by other synthetic narcotics, undetermined, subsequent encounter	T40.4X4D
Poisoning by other synthetic narcotics, undetermined, sequela	T40.4X4S
Poisoning by opioids	965.0
Poisoning by opium (alkaloids), unspecified	965.00
Poisoning by heroin	965.01
Poisoning by methadone	965.02
Poisoning by other opiates and related narcotics	965.09
Accidental poisoning by heroin	E850.0
Accidental poisoning by methadone	E850.1
Accidental poisoning by other opiates and related narcotics	E850.2

- Define the list of AUD codes

Alcohol abuse, uncomplicated	F10.10
Alcohol abuse, remission	F10.11
Alcohol abuse with intoxication, uncomplicated	F10.120
Alcohol abuse with intoxication delirium	F10.121
Alcohol abuse with intoxication, unspecified	F10.129
Alcohol abuse with alcohol-induced mood disorder	F10.14
Alcohol abuse with alcohol-induced psychotic disorder with delusions	F10.150
Alcohol abuse with alcohol-induced psychotic disorder with hallucinations	F10.151
Alcohol abuse with alcohol-induced psychotic disorder, unspecified	F10.159
Alcohol abuse with alcohol-induced anxiety disorder	F10.180
Alcohol abuse with alcohol-induced sexual dysfunction	F10.181
Alcohol abuse with alcohol-induced sleep disorder	F10.182
Alcohol abuse with other alcohol-induced disorder	F10.188
Alcohol abuse with unspecified alcohol-induced disorder	F10.19
Alcohol dependence, uncomplicated	F10.20
Alcohol dependence, in remission	F10.21
Alcohol dependence with intoxication, uncomplicated	F10.220
Alcohol dependence with intoxication delirium	F10.221
Alcohol dependence with intoxication, unspecified	F10.229
Alcohol dependence with withdrawal, uncomplicated	F10.230
Alcohol dependence with withdrawal delirium	F10.231
Alcohol dependence with withdrawal with perceptual disturbance	F10.232
Alcohol dependence with withdrawal, unspecified	F10.239
Alcohol dependence with alcohol-induced mood disorder	F10.24
Alcohol dependence with alcohol-induced psychotic disorder with delusions	F10.250

Alcohol dependence with alcohol-induced psychotic disorder with hallucinations	F10.251
Alcohol dependence with alcohol-induced psychotic disorder, unspecified	F10.259
Alcohol dependence with alcohol-induced persisting amnesic disorder	F10.26
Alcohol dependence with alcohol-induced persisting dementia	F10.27
Alcohol dependence with alcohol-induced anxiety disorder	F10.280
Alcohol dependence with alcohol-induced sexual dysfunction	F10.281
Alcohol dependence with alcohol-induced sleep disorder	F10.282
Alcohol dependence with other alcohol-induced disorder	F10.288
Alcohol dependence with unspecified alcohol-induced disorder	F10.29
Alcohol withdrawal delirium	291.0
Alcohol withdrawal	291.81
Acute alcoholic intoxication in alcoholism, unspecified	303.00
Acute alcoholic intoxication in alcoholism, continuous	303.01
Acute alcoholic intoxication in alcoholism, episodic	303.02
Acute alcoholic intoxication in alcoholism, in remission	303.03
Other and unspecified alcohol dependence	303.9
Other and unspecified alcohol dependence, unspecified	303.90
Other and unspecified alcohol dependence, continuous	303.91
Other and unspecified alcohol dependence, episodic	303.92
Other and unspecified alcohol dependence, in remission	303.93
Alcohol abuse	305.0
Alcohol abuse, unspecified	305.00
Alcohol abuse, continuous	305.01
Alcohol abuse, episodic	305.02
Alcohol abuse, in remission	305.03

- Drop naltrexone injections in the pre randomization period if there are not 2+ visits with an OUD/OD diagnosis (can be 1 OUD and 1 OD code) in the pre randomization period.
- Drop naltrexone injections in the post randomization period if there are not 2+ visits with an OUD/OD diagnoses (can be 1 OUD and 1 OD code) in the pre or post randomization period.
- Adjudicate subjects with both 2+ OUD/OD and 1+ AUD diagnosis codes to decide whether to include or exclude as OUD treatment.

16) Using the start and end dates of **each bup (including probuphine and sublocade) and naltrexone order or procedure** (and adding dispensed buprenorphine and/or methadone in a sensitivity analysis), create continuous episodes of use. This will result in a start and end date for each continuous OUD treatment. Continuous is defined as  $\leq 7$  days gap between end date and subsequent start date or  $\leq 14$  days gap if bup end date and XR injectable naltrexone start date (allow for washout period prior to starting XR injectable naltrexone). There may be multiple continuous episodes for any given subject because there will be gaps (see below) or breaks in continuous treatment.

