## **5.2.4 Sensitivity Analyses Focused on Assumptions Made in Estimating Patient-Years of OUD Medication Treatment (Objective 1: Main Implementation Outcome)**

While medication dispensings are only a proxy for ingestion of medications, they are the gold standard for ascertaining medication use with EHR and claims data. When evaluating patient days of OUD treatment, only medication orders are available at most PROUD health systems.

Pharmacy dispensings are complete at only one health system. Medication orders suffer from the same limitation of no assurance the medication was ingested plus medication orders could have been written and never dispensed. We expect that this is uncommon as preliminary data from Phase I at the health system with complete dispensings indicated 98% of patients with a buprenorphine order have a dispensing within 60 days of the order). However, medication dispensing data includes dispensed refills, but orders only include an indication that there can be a refill. Preliminary data from Phase I at this health system indicate approximately 14% of buprenorphine orders contain at least 1 refill on the order.

To address limitations of medication orders, we plan to conduct sensitivity analyses where we replicate the objective 1 main outcome analysis using different assumptions for calculating days of OUD medication treatment to see if there are changes in results and conclusion. Specifically, the sensitivity analyses below include more restrictive objective 1 outcome analyses with fewer assumptions about medication use and refills. In addition, we propose sensitivity analyses to address assumptions made in smoothing gaps between medication orders and/or procedures, a sensitivity analysis to add methadone maintenance therapy from the 1-2 health systems that have such data, and an analysis using dispensing data where available for at least some patients in both trial clinics within a health system.

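### Refill-inclusive supply of a buprenorphine order is credited without a check on the product, and no cleaning step acts on implausible refill counts

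*SAP*

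**What the plan says.** Appendix A1 explains that cleaning rules were written for missing fields and for "situations that would be very unlikely or impossible". One of its examples is a day's "supply greater than 6 months for a controlled substance". Section 4.1.1 step 1 undertakes to check the variables needed for the outcome and to impute implausible values. Step 2b of the same section adds refills to arrive at the total supply of the order.

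In Appendix A2 the supply variable rxsup is defined per fill: "an order for rxamt=30 that has PPD=2 would have a rxsup=30/2 or 15 days". The cleaning sequence is then:

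- Step 6 sets missing refills to 0.
- Step 7 tabulates anomalies, including a row for refills above 6.
- Step 8: "Output all bup orders for subjects with outliers (defined as above 3 x the 75th percentile) for rxsup and/or rxamt". Step 9 does the same for values of rxsup or rxamt below 1.
- Step 10 has a co-investigator review the orders identified.
- Step 11 sets values to missing, but only "For rxsup and rxamt outliers that are to be imputed" and for rxsup and rxamt values below 1.
- Step 12 imputes rxsup and rxamt and adds: "We do not need to impute refills, strength, ppd, or DD".
- Step 15 creates the end date: "If refills, multiply rxsup by number of refills +1 to calculate the end date".

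**The concern.** The quantity that enters the primary outcome is rxsup x (refills + 1), but only its first factor is screened and corrected. High refill counts are tabulated before and after imputation, and nothing in steps 11 and 12 permits them to be changed. An order can thus pass every check and still be credited with a supply that A1 gives as an example of implausible data.

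If the refill count is wrong and the patient has stopped, the excess becomes false days of treatment. The same algorithm produces the baseline covariate of the primary model. It also feeds the retention and treatment-duration measures in Section 4.3, where a false tail can create 6 months of retention, and the discontinuation measure, where it can hide a 60-day gap. The primary model has 12 clinic values on the raw scale, and Section 7.7 plans results by health system, so a clinic with very few treated days is sensitive to a single record.

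**Working it through.** **Inputs.** Refill rule: SAP A2 step 15. Plausibility limit: 6 months (A1), taken as 180 days, a cut point that Table 1a tabulates for per-fill rxsup. Phase 1 treated days per patient: SAP Table 3, FY2015-16. Clinic sizes: Protocol Table 2 (2016) and SAP Table 7.

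**1. Reproduce the plan's examples.** Credited days = rxsup x (refills + 1). Step 15: 30 x 2 = 60 and 30 x 3 = 90. Section 4.1.1: (60/2) x 3 = 90. All agree.

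**2. Fewest refills that exceed 180 days.**
- rxsup 28: 6 refills, 28 x 7 = 196
- rxsup 30: 6 refills, 30 x 7 = 210 (5 refills give exactly 180)
- rxsup 60: 3 refills, 60 x 4 = 240
- rxsup 90: 2 refills, 90 x 3 = 270

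None of these four has more than 6 refills, so none would even be counted in the tabulated refill row.

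**3. Does step 8 catch them?** The 75th percentile of rxsup is not given. If it is 30 (assumption), the screen flags rxsup above 3 x 30 = 90, and all four orders pass.

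**4. Illustrative error.** A 30-day order recorded with 11 refills instead of 1: 30 x 12 = 360 against 30 x 2 = 60, an excess of 300 days. This is hypothetical. It applies in full only if the patient has stopped, no later order covers the days, and at least 360 days of follow-up remain.

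**5. Scale.** The twelve FY2015-16 values sum to 3.230; 3.230/12 = 0.2692, or 2,692 days per 10,000 patients. The five lowest are 0.001, 0.002, 0.004, 0.019 and 0.021. The number of patients seen over the two follow-up years is not given, so three sizes are used: 10,000 (the scaling unit); 173,166/12 = about 14,430 (Protocol Table 2 mean, one year); and 291,136/12 = about 24,261 (SAP Table 7, pre-randomization period).

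| Patients per clinic | 300 days per 10,000 | Arm mean (divide by 6) | % of 2,692 | Phase 1 clinics with total below 300 days |
|---|---|---|---|---|
| 10,000 | 300 | 50 | 1.9% | 5 (10, 20, 40, 190, 210) |
| 14,430 | 208 | 35 | 1.3% | 4 (14, 29, 58, 274; the fifth is 303) |
| 24,261 | 124 | 21 | 0.8% | 3 (24, 49, 97; the fourth is 461) |

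**6. What 5.2.4.a reaches.** For patients with only oral orders it drops the last order of each episode with its refills, so a false tail on the last order disappears. It does not reach a bad order earlier in an episode. Suppose the 11-refill order is written on day 1, true supply ends on day 60, and the patient returns with a new order on day 300. Dropping the last order leaves the first in place, and the 239 false days from 61 to 299 remain.

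**The case against.** The best defence is Section 5.2.4.a. The excess matters mainly in patients who stopped, and for them the bad order is often the last, which is the order removed. That analysis also reports excluded days by arm and health system, so a sizeable problem would probably show. This stands as mitigation, but it is a sensitivity analysis. It leaves the primary outcome, baseline covariate and retention measures as they are, discards genuine last orders too, and misses the mid-episode case.

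A second defence is that step 10 refers to orders from steps 7 and 8, and step 7 includes the refill tables. The wording is ambiguous. Even on the generous reading, steps 11 and 12 give the reviewer no action to take on refills.

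Third, the 6-month remark could mean supply per fill. Section 4.1.1 step 2b, however, treats the refill-inclusive total as the supply of the order.

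Several stronger readings are tempting and not supported:
- That refills are not cleaned at all. Missing values are set to 0.
- That the percentile column of Table 2a is blind to refills. Section 5.2.4 reports that "approximately 14% of buprenorphine orders contain at least 1 refill on the order", from one health system in Phase 1. On that figure the 75th percentile is 0, so the column would count every order with a refill, and the maximum would be visible. It is uninformative as a cut-off, and no step acts on it.
- That the 180-day look-back in step 17 assumes no oral order lasts longer. It may simply reflect the 180 days assigned to the implant.
- That the trial result is biased. No frequency of high-refill orders is given, and there is no stated reason for errors to differ by arm. One order is small against the 5-fold increase targeted, or the 30% increase for which SAP Table 5 shows 84% power.

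**Conclusion.** The gap is real and comes from the order of the steps: the plausibility check covers the per-fill factor, the outcome uses the product, and Appendix A does not deliver what Section 4.1.1 step 1 states. A 30-day order with 6 or more refills is credited with more than 180 days.

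The effect on the arm comparison is probably small: 0.8% to 1.9% of the Phase 1 mean per 300-day excess, assuming 24,261 to 10,000 patients per clinic. Its frequency and direction are unknown. The effect on individual clinics and health-system tables can be large, since one such excess could exceed the two-year total of 3 to 5 of the 12 Phase 1 clinics over the same range. The figures assume a wrong refill count, no later order over the same days and enough remaining follow-up. This merits a correction to the algorithm; it does not call the design into question.

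**What to change.** Add to Appendix A2, after step 12:

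1. Compute rxsup x (refills + 1) for every oral buprenorphine order.
2. Send every order above 180 days to the step 10 co-investigator review, blind to arm, and correct the step numbers cited there.
3. Where the refill count is not confirmed, set it to missing and impute by the step 12 rule: the most common refill value in the same patient's orders within 100 days either side, otherwise 0. Going straight to 0 would be worse; in the example above, where the true value is 1, it would delete 30 valid days.
4. Report the number of orders changed, by arm and health system.

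Amend the step 12 sentence on refills so that it agrees with Section 4.1.1 step 1. The cost is a few lines of specification and a small amount of review. The downside is that some genuine long refill chains will be shortened if review cannot confirm them.
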